7.3 Safety and Toxicity Management

The Medical Monitor will be responsible for the overall safety monitoring of the study. The site PI will be responsible locally for safety. The Safety Monitoring Committee will review safety laboratory studies as delineated in Section 3.1.

Safety assessments include the following:

- Incidence of all adverse events classified by system organ class (SOC), preferred term, severity, and relationship to study treatment
- Changes in safety laboratory parameters (e.g., hematology, serum chemistry, and urinalysis)
- Local and systemic injection site review; special attention will be paid to the examination of the injection site. Administration site reactions and the participant's complaints will be documented.

7.3.1 Events Requiring Expedited Reporting

Events requiring expedited reporting (ERER) will be defined as any Adverse Event of Special Interest (see section 7.1.3) regardless of intensity or relationship to Study Treatment or any Study Treatment-related adverse events that follow:

- Grade 3 or greater administration site erythema, and/or induration recorded \geq 2 hours after Study Treatment;
- Grade 4 or greater administration site pain, tenderness recorded \geq 2 hours after Study Treatment;
- Grade 3 or greater fever;
- Grade 3 or greater systemic symptoms, including generalized pruritus;
- Grade 3 or greater laboratory abnormalities

As per the Toxicity Grade for Healthy Adults (Appendix B). The most severe grade for that particular event is to be documented in the CRFs.

Sites will inform the Sponsor of any ERER within 24 hours to discuss whether dosing to the participant should continue.

7.3.2 Stopping Rules (Criteria for Pausing of Study)

If any of the following situations occur then further enrollment and Study Treatments will be halted immediately until a thorough investigation has been conducted by the Medical Monitor and Principal Investigator and the IRB/REC (if applicable):

- One third (1/3) or more participants experience an ERER assessed as related to Study Treatment;
- Three or more participants in the same treatment arm discontinue due to an AE related to the Study Treatment;
- Any participant experiences a potentially life threatening AE, Grade 4 AE or death assessed as related to Study Treatment;
- Two or more participants within a treatment arm experience the same or similar grade 3 or 4 adverse event, assessed as related to Study Treatment;
- Seven or more participants across all treatment arms experience the same or similar grade 3 or 4 adverse event, assessed as related to Study Treatment;

- Any report of anaphylaxis of Grade 3 or greater assessed as related to Study Treatment.

Upon conclusion, the sponsor or designee will notify all investigators and IRBs/EC (if required) regarding the outcome of any investigation stemming from a Study Pause.

Any SAE or death assessed as related to Study Treatment will lead to an immediate halt of study enrollment and Study Treatments.

Guidelines for assessing relatedness are detailed in Section 7.1.6.

8. STATISTICAL CONSIDERATIONS

8.1 General Considerations

The statistical analysis of the data will be performed by GeneOne Life Science or its representative. Descriptive statistics will be presented from the data collected in this Phase I study.

For the baseline characteristics, we will present continuous variables as means, medians, standard deviations, and interquartile ranges, and categorical variables as frequencies and percentages.

Analysis populations will include:

Per-protocol (PP) analysis to comprise participants who receive all Study Treatments and have no protocol violations. Participants in this sample will be grouped to treatment arms as randomized.

The modified intention to treat (mITT) analysis includes all participants who receive at least one Study Treatment. Participants in this sample will be grouped to treatment arms as randomized. Analyses on the mITT sample will be considered supportive of the corresponding PP analyses.

The safety analysis set includes all participants who receive at least one Study Treatment. Participants will be analyzed as to the treatment they received.

Participants who do not complete the study will not be replaced.

8.2 Demographic and Other Baseline Characteristics

Demographic and baseline data, vital signs, medical history, concomitant illnesses, and current medications/treatments will be summarized by means of descriptive statistics: continuous variables as mean, median, standard deviation, and interquartile ranges and categorical variables as frequencies and percentages, stratified by treatment arm based on the mITT population.

8.3 Safety Analysis

8.3.1 Adverse events

Treatment emergent AEs will be summarized by estimates of proportions, exact 95% binomial CIs, and 95% CIs. The differences between the groups (proportions

and GMT ratio) will be calculated. We will use the chi-square test to evaluate the significance of the differences in frequency between groups. These frequencies will be presented separately by dose and overall, i.e. based on pooled doses, and will depict overall, by system organ class and by preferred term, the number and percentage of participants affected. Additional frequencies will be presented with respect to maximum severity and to strongest relationship to Study Treatment. Multiple occurrences of the same AE will be counted only once following a worst-case approach with respect to severity and relationship to Study Treatment. All serious AEs and administration site events will also be summarized as above.

For the purpose of summarizing the safety all active vaccine groups will be grouped together. The proportion of participants experiencing grade 3 or grade 4 adverse events following the vaccine will be presented. The precision with which this sample result estimates the rate of similar adverse events in the population represented by the study sample will be reported in terms of 95% confidence intervals (CI) around the sample proportions. This will provide 95% confidence that the rate of severe adverse effects is not greater than the upper limit of the CI around the proportion of participants with grade 3+ events in the study sample.

Table 8.3.1 illustrates the confidence intervals for a range of hypothetical proportions of adverse events. This table shows (e.g.) that a sample finding of no grade 3 or grade 4 adverse events in a total evaluable sample of 40 participants would provide 95% confidence that the rate in the population from which the sample was drawn is no greater than 8.8%.

Table 8.3.2 shows the probability of detecting at least 1 adverse event of a given type and/or level of severity in the study sample, given a range of hypothesized rates in the population from which the sample was drawn. The table demonstrates that the probability of observing one or more events in a sample of 40 participants is $\geq 70\%$ with events whose population probabilities are at least 2%, while the probability of observing two or more events is $\geq 34\%$ for events whose population probabilities are at least 3%.

Table 8.3.1: Exact 95% confidence intervals around potential proportions of participants exhibiting Grade 3+ adverse events (total sample and selected subsample sizes)

N	Samples Rate (%)	Lower Limit (%)	Upper Limit (%)
40	0	0	8.8
	1	0	10.7
	2	0	12.4
	3	0.1	13.9
	4	0.3	15.5
	5	0.6	16.9
	6	1.0	18.3
	7	1.4	19.7

	8	1.8	21.1
	9	2.3	22.4
	10	2.8	23.7

Table 8.3.2. Probability of detecting Adverse Events

True Event Rate in the Population Represented by the Study Sample	Probability of Observing Event(s) in the Study Sample (N = 40)	
	1 or more Event	2 or more Events
0.5%	18%	2%
1%	33%	6%
2%	55%	19%
3%	70%	33%
4%	80%	48%
5%	87%	60%

The main summary of safety data will be based on events occurring within 14 days of administration of Study Treatment (as specified in Section 9.6.1).

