8.5 Sample Size

See section 8.3 for a power calculation of the probabilities of observing adverse events and immunological responses in the present trial.

With 40 participants receiving vaccine at any level, the study provides 80% probability of detecting an event if the incidence is greater than 4% in the vaccinated population (**Table 8.4.1**).

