3.6. DETERMINATION OF SAMPLE SIZE

As indicated in protocol section 8.3 and 8.4 for the probabilities of observing adverse events and immunological responses in the present trial, a sample finding of no grade 3 or grade 4 adverse events in a total evaluable sample of 40 participants would provide 95% confidence that the rate in the population from which the sample was drawn is no greater than 8.8%. With 40 participants receiving vaccine at any level, the study provides 80% probability of detecting an event if the incidence is greater than 4% in the vaccinated population (shown in table below).

True Event Rate in the Population Represented by the Study Sample	Probability of Observing Event(s) in the Study Sample (N = 40)	
	1 or more Event	2 or more Events
0.5%	18%	2%
1%	33%	6%
2%	55%	19%
3%	70%	33%
4%	80%	48%
5%	87%	60%

In immunogenicity analysis, a sample finding of 75% responders in the total sample of 40 participants would provide 95% confidence that the rate in the population from which the sample was drawn was no lower than 61% (Shown in table below).

N	Sample rate	Lower Limit	Upper Limit
40	25%	14%	39%
	50%	36%	64%
	75%	61%	86%
	90%	79%	97%
	95%	85%	99%

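### Protocol 8.3.1 claims at least a 70% chance of seeing one or more events at a 2% true rate; its own table, SAP 3.6 and the binomial give 55%, and 70% only at about 3%

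*Protocol*

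**What the plan says.** The sentence in Protocol 8.3.1 reads, in its first part, "The table demonstrates that the probability of observing one or more events in a sample of 40 participants is" 70% or more "with events whose population probabilities are at least 2%, while the probability of observing two or more events is" 34% or more "for events whose population probabilities are at least 3" percent.

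The table it describes, headed "Table 8.3.2. Probability of detecting Adverse Events", is for N = 40. Its 2% row gives 55% for one or more events and 19% for two or more. Its 3% row gives 70% and 33%.

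SAP 3.6 opens with "As indicated in protocol section 8.3 and 8.4 for the probabilities of observing adverse events" and reprints the table with identical entries. It does not repeat the sentence.

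Protocol 8.5 says "See section 8.3 for a power calculation of the probabilities of observing adverse events" and immune responses. It then adds that "the study provides 80% probability of detecting an event if the incidence is greater than 4% in the vaccinated population", but points to Table 8.4.1 for this, which holds immune-response intervals.

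**The concern.** The sentence claims to report what Table 8.3.2 shows, and the table shows something else. A reader of the protocol finds two answers for the chance of detecting an event with a 2% true rate: 70% or more in the text, and 55% in the table.

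This matters because safety is the primary objective, the product has no earlier human experience (Protocol 1.1.5), and the plan has no hypothesis-based sample-size calculation. The detection probabilities in 8.3 are the justification offered for 40 participants. An ethics committee member or report author who quotes the text would carry forward a claim that this design does not support.

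**Working it through.** **Inputs**

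- N = 40, doses pooled: Protocol 8.3.1, Table 8.3.2 and SAP 3.6.
- Text: one or more events, 70% or more, at a true rate of 2% or above; two or more events, 34% or more, at 3% or above.
- Tables: 55% and 19% at 2%; 70% and 33% at 3%.

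**Formulas** (independent participants, true rate p)

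- P(at least 1) = 1 − (1 − p)^40
- P(at least 2) = 1 − (1 − p)^40 − 40·p·(1 − p)^39

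**Step 1: reproduce the plan's table**

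| True rate | ≥1, printed | ≥1, exact | ≥2, printed | ≥2, exact |
|---|---|---|---|---|
| 0.5% | 18% | 18.2% | 2% | 1.7% |
| 1% | 33% | 33.1% | 6% | 6.1% |
| 2% | 55% | 55.4% | 19% | 19.0% |
| 3% | 70% | 70.4% | 33% | 33.8% |
| 4% | 80% | 80.5% | 48% | 47.9% |
| 5% | 87% | 87.1% | 60% | 60.1% |

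Eleven of the twelve cells equal the rounded exact value. The exception is two or more events at 3%: the exact probability is 0.3385, which rounds to 34%, and 33% is printed.

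**Step 2: test the text's 70% at 2%**

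- 0.98^40 = 0.4457, so P(at least 1) = 1 − 0.4457 = 55.4%.
- Overstatement: 70 − 55.4 = 14.6 percentage points.
- Chance of seeing no event at a 2% rate: 44.6%. The text implies 30% or less.

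**Step 3: look for a reading that gives 70% at 2%**

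- Poisson approximation: 1 − exp(−0.8) = 55.1%.
- One arm of 20: 1 − 0.98^20 = 33.2%.
- Counting vaccinations instead of participants, 40 × 3 = 120: 1 − 0.98^120 = 91.2%.
- The N that gives 70% at 2%: ln 0.3 / ln 0.98 = 59.6, so 60. No group in this trial has that size.
- The rate that gives 70% with N = 40: 1 − 0.3^(1/40) = 2.97%, in effect the table's 3% row.

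None of these readings supports the text. The obvious explanation is that 2% was written where 3% was meant.

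**Step 4: the second half of the sentence**

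At 3%, P(at least 2) = 33.8%, and 34% is first reached at a rate of 3.01%. So 34% or more is true only after rounding, and the tables' 33% is a rounding slip.

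**Step 5: the related statements**

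- 80% at a 4% rate (Protocol 8.5, SAP 3.6): exact 80.5%, correct.
- Upper 95% limit of 8.8% with 0 events in 40 (Protocol 8.3.1, SAP 3.6): exact 8.81%, correct.

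**The case against.** The best case on the other side is that this is a one-digit slip with no consequence. The correct table follows directly after the sentence. The SAP carries only correct one-event figures. The statements that carry most weight, 80% at 4% and the 8.8% bound, are right. Safety is summarised with exact intervals and nothing is tied to a 2% rate. The gap between 33% and 34% is less than one point, and the text is right there at whole-percent precision.

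Most of this stands as a limit on the effect. A reader of the SAP alone is not misled about a 2% event, and the 33%/34% difference would not deserve a comment by itself. The figure of 60 participants serves only to show that no sample in the trial yields the claim; neither document sets 70% at 2% as a target, so it is not a shortfall in sample size. What the objection does not do is make the sentence true. It is a false statement about detection under the primary objective, in the section that the protocol names as its power calculation.

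**Conclusion.** The concern holds. The 70% at 2% in Protocol 8.3.1 is wrong by about 15 percentage points: the correct figure is 55.4%, and 70% needs a true rate of about 3%. The two-event figure at 3% is a rounding matter only (33.8% exact). The calculation assumes all 40 participants are evaluable and independent, each with the same event probability, which is the basis of the plan's own table. Fewer evaluable participants would lower the 55%. This should be corrected, but it leaves the design, sample size, stopping rules and analyses untouched.

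**What to change.** In Protocol 8.3.1, change the rate for the one-or-more-events claim from 2% to 3%, or keep 2% and state 55%. In the same sentence, give the two-or-more-events probability at 3% as about 34%. Change that cell from 33% to 34% in Protocol Table 8.3.2 and in the SAP 3.6 table.

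Two optional editorial changes could go in at the same time:

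- In Protocol 8.5, point the 80%-at-4% statement to Table 8.3.2 instead of Table 8.4.1.
- In Table 8.3.1, use counts that can occur with 40 participants: 0/40 (0 to 8.8%), 1/40 (0.1 to 13.2%), 2/40 (0.6 to 16.9%), 3/40 (1.6 to 20.4%) and 4/40 (2.8 to 23.7%). This is for readability.

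The cost is one sentence and one table cell in the protocol and one table cell in the SAP, plus the optional edits if taken up. The stated chance of detecting a 2% event becomes less favourable.

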8.3.2 Laboratory Data

Continuous response variables per time point and changes from baseline will be summarized with mean, median, minimum, and maximum values. Categorical response variables will be summarized per time point with percentages. These will be calculated according to treatment arm.

8.4 Immunogenicity analysis

Data classified as positive/negative or responder/non-responder will be analyzed as the frequency of response for each assay within treatment arm at each time point at which an assessment is performed. For secondary immunogenicity outcomes, estimates of proportions and exact 95% binomial CIs and 95% CIs for the differences between the groups (proportions and geometric mean test (GMT) ratio) will be calculated. We will use the chi-square test to evaluate the significance of the differences between groups. For GMT and mean fold increase in GMT, we will calculate the mean and 95% CI for the log10-transformed titers and then transformed back to the original units by exponentiation. We will use the t test to compare the GMTs between groups. The proportion of participants meeting the criteria for immunologic response following vaccination will be presented for each study arm. The precision with which this sample result estimates the rate of immunologic response rates in the population represented by the study sample will be reported in terms of 90% CIs around the sample proportions. This will provide 95% confidence that the rate of immune response is not less than the lower limit of the proportion of study participants meeting immune response criteria. The primary immunogenicity analysis will include all subjects having evaluable data.

Table 8.4.1 illustrates the confidence intervals for a range of hypothetical proportions of immunologic response. This table shows (e.g.) that a sample finding of 30 (75%) responders in the total sample of 40 participants would provide 95% confidence that the rate in the population from which the sample was drawn was no lower than 62%.

The rate of response in arms will be compared using the chi-square test. Comparison between treatment arms will be carried out using a Mann Whitney U test for continuous variables, and a Fisher's Exact Test or Pearson's Chi-square Test for categorical factors. Because the study is small the study is underpowered for comparisons between arms.

Table 8.4.1: Exact 90% confidence intervals around potential proportions of participants achieving immunologic response criteria for each study arm (total sample and selected subsample sizes)

N	Sample rate	Lower Limit	Upper Limit
40	25%	14%	39%
	50%	36%	64%
	75%	61%	86%
	90%	79%	97%
	95%	85%	99%

The primary immunogenicity analysis will include all participants having evaluable data. A secondary qualitative analysis will assess immune responses relative to presence of pre-existing antibodies to other flaviviruses (West Nile or dengue) or chikungunya virus.

8.5 Sample Size

See section 8.3 for a power calculation of the probabilities of observing adverse events and immunological responses in the present trial.

With 40 participants receiving vaccine at any level, the study provides 80% probability of detecting an event if the incidence is greater than 4% in the vaccinated population (**Table 8.4.1**).

8.6 Missing Values

Missing data will not be replaced, and calculations will be done on reported values.

8.7 Interim analyses

No formal interim analyses will be performed for this study.

9. DATA COLLECTION, MONITORING, AND AE REPORTING

9.1 Confidentiality

Information about study participants will be kept confidential to the best of the study site's ability.

In the event that a participant revokes authorization to collect or use personal health information (PHI), the sponsor retains the ability to use all information collected prior to the revocation of participant authorization. For participants that have revoked

authorization to collect or use PHI, attempts should be made to obtain permission to collect at least vital status (i.e., that the participant is alive) at the end of their scheduled study period.

9.2 Source Documents

Source data is all information, original records or clinical findings, observations, or other activities in a clinical trial necessary for the reconstruction and evaluation of the trial. Source data are contained in original source documents. Examples of these original documents, and data records include: hospital records, clinical and office charts, laboratory notes, memoranda, participant's diaries or evaluation checklists, pharmacy dispensing records, recorded data from automated instruments, copies or transcriptions certified after verification as being accurate and complete, microfiches, photographic negatives, microfilm or magnetic media, x-rays, participant files, and records kept at the pharmacy, at the laboratories, and at medical records and within information technology systems that are involved in the clinical trial.

Monitoring of the clinical trial will be performed by experienced monitors, who will report to the Sponsor or the Sponsor designee. Records for all clinical participants in this trial will be monitored. Monitoring functions and activities are outlined in the separate Monitoring Plan.

9.3 Records to be kept

CRFs will be provided for each study participant. Participants must not be identified by name on any CRF. Participants will be identified by their participant identification number (PID).

9.4 Records Retention

It is the investigator's responsibility to retain study essential documents as per country regulations: in the US for at least 2 years after the last approval of a marketing application in their country and until there are no pending or contemplated marketing applications in their country or at least 2 years have elapsed since the formal discontinuation of clinical development of the investigational product. The sponsor will inform the investigator/institution as to when these documents are no longer needed to be retained; and 25 years for Canada.

9.5 Safety and Quality Monitoring and Record Availability

Monitoring

Monitoring of the clinical trial will be performed by experienced monitors, who will report to the Sponsor or the Sponsor designee as outlined in the Monitoring Plan.:

Record availability and auditing

The investigator will make study documents (e.g., ICFs, drug accountability forms, CRFs) and pertinent hospital or clinic records readily available for inspection by the local IRB/EC, the site monitors, regulatory agencies, GeneOne Life Science, Inc. or its designee for confirmation of the study data.

Participation as an investigator in this study implies acceptance of potential inspection by regulatory authorities and applicable compliance and quality assurance offices.

9.6 Adverse Experience (AE) Reporting

To assure the safety of the participants, information about all AEs (see Section 7.1 Safety Parameters for definitions), whether volunteered by the participant, discovered by investigator or study staff questioning, or detected through physical examination, laboratory test or other means, will be collected and recorded in the participant's source documents and followed as appropriate.

In addition to AE reporting, a summary of the study's overall progress will be forwarded to regulatory agencies according to the local requirements (e.g., every 6 months, annual).

9.6.1 Study Reporting Period of Adverse Events

All solicited and unsolicited adverse events will be collected throughout the study and recorded on the CRFs. The Study Report will analyze and summarize all adverse events throughout the study. Unsolicited AEs will be summarized for the 14 day period following each administration of Study Treatment. See next section for SAEs.

9.6.2 Study Reporting Period of Serious Adverse Events

The reporting period for SAEs (without regard to causality) is the entire period following the signing of the informed consent form until the end of the study.

Each AE will be assessed to determine whether it meets seriousness criteria. If the AE is considered serious, the investigator should record this event to GeneOne Life Science within 24 hours of becoming aware of the event. The investigator may also directly report this event to the clinical site IRB/EC per standard operating procedures within 24 hrs.

Expectedness of SAEs will be determined by GeneOne Life Science using reference safety information specified in the Investigator's Brochure. An event may qualify for expedited reporting to regulatory authorities if it is an SAE, unexpected per reference safety information and considered related following the guidelines in Section 7.1.4 (Suspected Unexpected Serious Adverse Reaction, SUSAR) in line with relevant legislation. All investigators will receive a safety letter notifying them of relevant SUSAR reports. The investigator should notify the Ethics Committee as soon as is practical, of serious events in writing where this is required by local regulatory authorities, and in accordance with the local institutional policy.

At any time after completion of the SAE reporting period, if an investigator becomes aware of an SAE that is suspected by the investigator to be related to the study drug, the event will be reported to the Sponsor or its designee.

If the investigator becomes aware of an SAE, an AESI, or an MAAE in a study participant after the last scheduled follow-up visit, and considers the event related to prior Study Treatment, the investigator will report it to GeneOne Life Science.

SAE TELEPHONE AND CONTACT INFORMATION:

MEDICAL MONITOR:	[name] PhD MBA	MAILING ADDRESS:
[contact]p; [contact] c	GeneOne Life Science, Inc.
SAFETY [contact]	[name]
[contact]	[name]
EMAIL:	[contact]	[name]

The report should contain as much clinical safety information as possible, but at minimum, the initial report must include the following information:

- Event
- Study code
- Participant number, initials and date of birth
- Investigational study product
- Reporter name and contact information

In the case of a “minimum report” (one that is solely comprised of the information bulleted above), a more detailed follow-up report will be sent as soon as more information becomes available but no later than 7 calendar days after the date of the initial report. Each SAE must be followed up until resolution or stabilization and for a reported death, the investigator will supply GeneOne Life Science and the Ethics Committee with any additional requested information (e.g., autopsy reports and terminal medical reports).

The original SAE form must be kept at the study site. GeneOne Life Science or its representative will be responsible for determining and in turn, reporting SAEs to regulatory authorities according to the applicable regulatory requirements.

SAEs must be followed by the investigator until resolution, even if this extends beyond the study-reporting period. Resolution of an SAE is defined as the return to baseline status or stabilization of the condition with the expectation that it will remain chronic.

